## 7. RATIONALE AND BACKGROUND

Urothelial Cancer (UC) accounts for approximately 90% of all cancer of urinary tract (bladder, upper urinary tract, urethra). About 11 000 patients are newly diagnosed with an urinary tract cancer each year in France. Patients with metastatic UC have a dismal prognosis with a five-year survival rate of only 5%. Platinum-based polychemotherapy regimen is currently the first-line standard of care for patients with advanced/metastatic disease, but despite high initial response rates, durable and complete responses following first-line chemotherapy (ChT) are uncommon, and most patients will ultimately experience disease progression within nine months after initiation of treatment.

Avelumab (MSB0010718C, BAVENCIO®) is a human Immunoglobulin G1 monoclonal antibody directed against the programmed death ligand1 (PD-L1).

Avelumab in combination with Best Supportive Care (BSC) as a maintenance treatment had been evaluated versus BSC alone in a phase III randomized trial (JAVELIN Bladder 100) for locally advanced or metastatic Urothelial Carcinoma (adv/mUC) patients who have not progressed with first-line platinum-based chemotherapy. The JAVELIN Bladder 100 study has demonstrated a significant 7.1-months improvement in median Overall Survival with Avelumab+BSC as first-line maintenance versus BSC alone, with a 31% reduction of the death risk in the overall population (hazard ratio = 0.69 (95% CI, 0.56, 0.86), p<0.001). The results of the JAVELIN Bladder 100 had been presented at ASCO 2020 and published in the New England Journal of Medicine on September 18th, 2020.

On June 30th, 2020, U.S. Food and Drug Administration approved avelumab for maintenance treatment of patients with locally advanced or metastatic Urothelial Carcinoma who have not progressed with first-line platinum-containing chemotherapy.

On July 3rd, 2020 the French National Agency for Medicines and Health Products issued a cohort Temporary Authorization for Use (ATU) extension for avelumab in the first-line maintenance treatment of adult patients with locally advanced or metastatic Urothelial Carcinoma who have not progressed with first-line platinum-based chemotherapy and presenting an ECOG performance status of 0 or 1.

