On December 11th, 2020 the CHMP has adopted a positive opinion for avelumab as first line maintenance treatment of adult patients with locally advanced or metastatic urothelial carcinoma whose disease has not progressed with platinum-based induction chemotherapy. Marketing authorization for avelumab use in adv/mUC was issued on January 21st, 2021 by European Medicine Agency.

The early use in France of avelumab in maintenance treatment for adv/mUC patients in the setting of the the ATU is an opportunity to early collect real world data of avelumab in this indication.

In addition to confirm the effectiveness and safety data provided by JAVELIN Bladder 100 study in routine clinical practice this non-interventional study is an opportunity to generate effectiveness and safety data on different subgroups of interest. The main subgroup of interest will be the adv/mUC patients with histological variants. Few data are available on the efficacy of immunotherapy in histology variants of adv/mUC.

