### 9.2.1. Inclusion criteria

Patients must meet all of the following inclusion criteria to be eligible to the study:

1. Patient  $\geq 18$  years of age
2. Patient with locally advanced or metastatic urothelial carcinoma (irrespective of tumor histology) whose disease has not progressed (ongoing stable disease, partial response or complete response) following completion of first-line platinum-based chemotherapy and who has been (retrospective), is (retrospective and prospective), will be (prospective) treated with avelumab.
3. For a patient alive at the moment of the inclusion in the study : the patient must be informed of the study, he/she must be given an information letter signed by the investigator and must not be opposed to the collection of his/her data

For a patient who died before the inclusion in the study : the patient (during his lifetime) must not be opposed in writing to the collection of his data. 4. Patient benefiting from a social security scheme according to local regulations

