## **9.9. Limitations of the research methods**

### **9.9.1. Selection bias**

#### Centers selection

Both specialized centers in adv/mUC management and non-specialized public and private centers have included patients in the avelumab ATU and will therefore be contacted to participate in the study. If the representativeness of the sample in relation to all patients treated with avelumab for adv/mUC in France over the study period cannot be guaranteed, this multicenter selection will make it possible to minimize this bias.

In addition, the characteristics of participating centers and contacted centers will be compared (i.e local public hospitals, private centers, expert centers, university hospitals), and in case of difference, adjustment on the type of centers could be done to provide corrected estimates of primary and secondary endpoints as sensitivity analysis.

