5.3 SUBGROUPS

The primary and secondary objectives will be evaluated on the overall population and for prespecified subgroup.

- Main subgroup of interest: histology (UC with variant; UC without variant).
- Other subgroups of interest:
 - Histology (Pure UC; UC with variant, Pure adenocarcinoma, Other, Missing)
 - ECOG at avelumab initiation (PS 0-1; PS ≥ 2),
 - Locally advanced urothelial carcinoma versus metastatic urothelial carcinoma,
 - Previous ChT regimens (Cis/Gem, Carbo/Gem, Cis/Carbo/Gem, MVAC regimens, others),
 - Best response to 1st line chemotherapy (CR, PR, SD)
 - Regrouped best response to 1st line chemotherapy (CR+PR, SD),
 - Number of ChT cycles received in 1st line (< 4 cycles; ≥ 4 cycles and ≤ 6 ; > 6 cycles), Site of baseline metastases before ChT (visceral vs non-visceral),
 - Participants with an early relapse on avelumab and participants with a long-term response to avelumab. Patient is considered as early progressor if PFS is less than 3 months and if progression is observed. Patient is considered as long responder if PFS is equal or higher than 12 months, whatever the outcome.
This subgroup of interest will be used only for Overall Survival and progression free survival analyses, and baseline characteristics.
 - Delay between the end of ChT and the start of avelumab (< 4 weeks; between 4 and 10 weeks; > 10 weeks),
 - Delay between the end of ChT and the start of avelumab (< 4 weeks; ≥ 4 weeks),
 - ATU participants versus non ATU participants, site for the primary tumor (bladder, urethra, upper tract),
 - PD-L1 status,
 - FGFR abnormality,
 - Bajorin risk classification evaluated before ChT 1st line (0, 1, 2),
 - Presence of biological anomalies (neutropenia, lymphopenia, impaired renal function, anemia),
 - Use of concomitant treatments (corticosteroids/AIS/NSAIDs, sartans/ACE inhibitors, antibiotics, PPI) at avelumab initiation,
 - Type of subsequent treatment: Antibody-Drug Conjugate (ADC) treatment, chemotherapy, immunotherapy, targeted therapy, other. This classification will be made thanks to a medical review from Pfizer team.
 - Type of subsequent treatment: ADC versus Other.

PFIZER CONFIDENTIAL

CT24-WI-GL03-RF02 2.0 Non-Interventional Statistical Analysis Plan For Primary Data Collection Study

01-Jun-2020

Page 11 of 28

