8.1.3 Analysis of time-to-event data

Kaplan-Meier estimates (product-limit estimates) will be presented together with a summary of associated statistics including the median survival time with 2-sided 95% CIs. In particular, the survival rate at 3, 6, 9, 12, 15, 18 and 24 months will be estimated with corresponding 2-sided 95% CIs. The CIs for the median will be calculated according

PFIZER CONFIDENTIAL

CT24-WI-GL03-RF02 2.0 *Non-Interventional Statistical Analysis Plan For Primary Data Collection Study*

01-Jun-2020

Page 15 of 28

to Brookmeyer and Crowley (Brookmeyer R, 1982) and the CIs for the survival function estimates at the time points defined above will be derived using the log-log transformation according to Kalbfleisch and Prentice (Kalbfleisch JD, 2002) (conftype=loglog default option in SAS Proc LIFETEST) with back transformation to a CI on the untransformed scale. The estimate of the standard error will be computed using Greenwood's formula.

Frequency (number and percentage) of participants with each event type and censoring reasons will be presented.

For each subgroup analysis, comparison of the different modalities to a reference level will be performed using univariate Cox proportional hazard models. Ties will be handled using the Exact option in SAS (Ties=Exact option in SAS PROC PHREG). Results will be expressed in terms of hazard ratios (HR) and a 2-sided 95% CI will be associated to each HR. A HR of 1 equals a lack of association, a HR greater than 1 suggests an increased risk compared to the reference level, and a HR below 1 suggests a decreased risk.

Time of follow-up for each event (OS and PFS)

A Kaplan-Meier estimation for follow-up duration will also be generated to assess the follow-up time reversing the censoring and event indicators.

Handling of left truncation and right censoring:

The overall survival from the first injection of the chemotherapy used in 1st line will cover

a retrospective and/or prospective data collection period. The time to event of interest ("survival" time) or censoring if no event occurs (right censoring) will be based on the 1st line of chemotherapy start date at a time-point preceding the study entry (avelumab start date). As a result, only participants who are still alive are included in the study.

Therefore, the time from 1st line of chemotherapy start date to avelumab start date is called immortal time and corresponds to a left truncation in survival analyses.

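### The ATU versus non-ATU hazard ratio is confounded with performance status, because the ATU admitted only ECOG 0-1 and later access had no ECOG limit

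*SAP*

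**What the plan says.** - **ATU access.** Protocol section 7 says the cohort ATU extension of July 2020 was for patients "presenting an ECOG performance status of 0 or 1". SAP section 2 repeats this.
- **Later access.** Protocol section 7 describes the indication that followed as "first line maintenance treatment of adult patients with locally advanced or metastatic urothelial carcinoma whose disease has not progressed with platinum-based induction chemotherapy". No ECOG condition is mentioned.
- **Study eligibility.** The disease criterion in protocol 9.2.1 reads "irrespective of tumor histology) whose disease has not progressed (ongoing stable disease, partial response or complete response"). None of the inclusion or exclusion criteria refers to ECOG.
- **ECOG ≥2 patients are expected.** SAP 5.3 prespecifies "ECOG at avelumab initiation (PS 0-1; PS ≥ 2") as a subgroup.
- **The contrast.** SAP 5.3 also prespecifies "ATU participants versus non ATU participants, site for the primary tumor (bladder, urethra, upper tract"). The bullet runs two subgroups together, which is only a matter of layout.
- **The model.** SAP 8.1.3 says that for each subgroup analysis "comparison of the different modalities to a reference level will be performed using univariate Cox proportional hazard models". It then tells the reader how to take the result, for example that "a HR below 1 suggests a decreased risk".
- **Adjustment.** The summary table in SAP 8.2.5 shows no covariates or strata for any outcome. The only adjustment mentioned is optional and concerns centers (protocol 9.9.1): "adjustment on the type of centers could be done to provide corrected estimates of primary and secondary endpoints as sensitivity analysis".

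**The concern.** Any observational subgroup contrast may be unbalanced. This one is unbalanced by rule. The access terms kept ECOG ≥2 patients out of one arm of the comparison, and the plan itself treats that characteristic as a subgroup factor. If ECOG ≥2 patients die sooner, the non-ATU group will show worse survival even if access route makes no difference in comparable patients.

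The plan attaches a risk interpretation to each HR and runs interim analyses for publication, so a reader could take the result as a property of the access route. More patients would narrow the interval around the distorted value without moving it. The univariate Cox rule reaches the time-to-event endpoints that SAP 8.2 reports by subgroup: OS, progression-free survival (PFS), duration of response and duration of treatment.

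**Working it through.** **The plan's own figure.** The documents give no figure for the ATU contrast. Their one precision calculation (protocol 9.5) checks the survival model used below. It assumes exponential survival with mean 29 months, so the median is m = 29 × ln 2 = 20.1 months. With n patients and no censoring, the 95% limits for the median are 2nm/χ²(0.975; 2n) and 2nm/χ²(0.025; 2n).

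- n = 600: 1200 × 20.1/1297.9 = 18.6 and 1200 × 20.1/1105.9 = 21.8. The protocol states 18.6 and 21.8.
- n = 47: 15.4 and 27.4, as stated.

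**Inputs for the contrast**

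- From the documents: N = 600; survival S(t) = exp(−t/29) for ECOG 0-1 patients (protocol 9.5, where it is given for all patients); no ECOG ≥2 patients in the ATU group (access terms).
- Assumed, because the documents do not give them: share p of ECOG ≥2 among non-ATU patients, 2-20%; death HR R for ECOG ≥2 versus 0-1, 2.0-2.5; ATU share q, 30-70%; follow-up uniform over 24-42 months.
- Null condition: access route has no effect on survival.

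**Formulas**

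- ATU group: S_A(t) = exp(−t/29).
- Non-ATU group: S_N(t) = (1−p)·exp(−t/29) + p·exp(−R·t/29).
- The large-sample univariate Cox log HR β (non-ATU versus ATU) solves ∫ G(t)·[(1−q)·f_N·(1−w) − q·f_A·w] dt = 0. Here w = (1−q)·S_N·e^β / [(1−q)·S_N·e^β + q·S_A], the f are the densities, and G(t) is the probability of still being under follow-up.
- Upper limit: at t = 0 the hazard ratio is 1 + p(R−1), for example 1 + 0.10 × 1.0 = 1.10. It falls afterwards as ECOG ≥2 patients die sooner, so the fitted HR lies between 1 and this value.
- Approximate standard error of log HR with D deaths: 1/√(D·q·(1−q)).

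**Results, no true ATU effect, q = 50%**

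| p | R | HR non-ATU vs ATU | Deaths of 600 | Approx. 95% CI |
|---|---|---|---|---|
| 2% | 2.0 | 1.01 | 406 | 0.83-1.23 |
| 2% | 2.5 | 1.02 | 406 | 0.84-1.24 |
| 5% | 2.0 | 1.03 | 408 | 0.85-1.25 |
| 5% | 2.5 | 1.04 | 409 | 0.86-1.27 |
| 10% | 2.0 | 1.07 | 411 | 0.88-1.30 |
| 10% | 2.5 | 1.09 | 412 | 0.90-1.32 |
| 20% | 2.0 | 1.14 | 418 | 0.94-1.38 |
| 20% | 2.5 | 1.18 | 420 | 0.98-1.43 |

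An ATU share of 30% or 70% gives the same HRs to two decimals, and every interval still includes 1.

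**Exceptions to the access rule.** If 3% of ATU patients were nevertheless ECOG ≥2 (q = 50%), the four HRs at p = 10-20% become 1.05, 1.06, 1.12 and 1.15. The distortion shrinks but keeps its direction.

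**Restriction to ECOG 0-1.** Both groups then have S(t) = exp(−t/29), and the HR is 1.00.

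**The case against.** The strongest reply is that the SAP has no hypotheses and calls its analyses purely descriptive. ATU status is one of many secondary subgroups, all compared univariately. If the aim is to describe survival under each access route, the case mix belongs to the answer, and a restricted analysis answers a different question. OS and PFS by ECOG are planned anyway. The general statement in SAP 5.3, that the objectives are evaluated by subgroup, could be read to include ECOG by ATU status.

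Part of this stands. The all-patient contrast is a valid description of who was treated under each route and should stay. The descriptive label does not settle the matter, because SAP 8.1.3 reads each HR as increased or decreased risk. The baseline breakdowns named in SAP 8.2.4 and 8.2.5 do not include ATU status. What sets this contrast apart from the others is the access rule.

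The documents do not support four stronger readings that a reader might infer:

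- *Every ECOG ≥2 patient is non-ATU.* This follows from the access terms, not from data. The documents do not define ATU participants, and the ECOG subgroup uses status at avelumab initiation, so exceptions are possible.
- *The contrast tests whether early-access results hold in later use, so the distortion would show falling effectiveness after marketing.* No section gives the contrast that purpose.
- *Every endpoint gets a distorted HR.* The Cox rule covers time-to-event endpoints. Response rate is a proportion with an exact interval. SAP 8.2.2 has no subgroup statement for OS from chemotherapy start or for PFS2, and the table in 8.2.5 cites section 5.3 only for OS.
- *The distortion is large.* It depends on two figures that the documents do not give, and it is negligible if few ECOG ≥2 patients enroll.

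**Conclusion.** The concern holds for the interpretation of one secondary contrast. By the terms of access, the ATU versus non-ATU HR is confounded with performance status, and nothing in the plan restricts, adjusts or cautions against it.

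With no true effect of access route, the non-ATU versus ATU HR for OS would be about 1.01-1.04 at 2-5% ECOG ≥2 and 1.07-1.18 at 10-20%. These figures rest on an assumed death HR of 2.0-2.5, exponential survival and 24-42 months of follow-up. In each case the approximate interval includes 1, so the distortion alone would not usually look conclusive. It has a fixed direction and does not shrink with sample size. The primary estimate of OS in the whole cohort does not depend on this contrast.

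**What to change.** In SAP 5.3 and 8.1.3:

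1. Add the ATU versus non-ATU Kaplan-Meier and Cox comparison in patients with ECOG 0-1 at avelumab initiation, and name it as the HR to interpret.
2. Keep the all-patient contrast, labelled as descriptive only.
3. Show non-ATU ECOG ≥2 patients as a separate group if there are at least 10, in line with the SAP's own minimum.
4. Tabulate ECOG at initiation by ATU status.
5. Define ATU participants.
6. State that calendar period and other case-mix differences remain after the restriction.

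The cost is a few lines of SAP text and some additional output. ECOG at initiation is already collected (protocol Table 2). The restricted contrast loses the ECOG ≥2 patients and, in either group, those with missing ECOG, so its interval will be slightly wider.

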6 ENDPOINTS AND COVARIATES

6.1 EFFICACY/EFFECTIVENESS ENDPOINT(S)

6.1.1 Time-to-event endpoints

Variable	Role	Data source(s)	Operational definition
Overall Survival (OS)	Time to Event Outcome (primary endpoint)	Patient medical records and CRF	Time (month) from the first injection of avelumab to death, whatever the reason +1
Overall Survival 2	Time to Event Outcome (secondary endpoint)	Patient medical records and CRF	Time (month) from the first injection of the chemotherapy used in 1st line to death, whatever the reason +1
Progression Free Survival (PFS)	Time to Event Outcome (secondary endpoint)	Patient medical records and CRF	Time (month) from the first injection of avelumab to the date of progression or death from any cause +1.
Progression Free Survival (PFS) 2	Time to Event Outcome (secondary endpoint)	Patient medical records and CRF	Time (month) from the first injection of avelumab to the date of progression or death from any cause during the 2nd line of treatment post-avelumab +1.
Objective Response Rate (ORR)	Outcome (secondary endpoint)	Patient medical records and CRF	Proportion of patients with a Complete Response (CR) or Partial Response (PR) as a best response during the avelumab treatment.
Duration Of Response uber avelumab (DOR)	Time to Event Outcome (secondary endpoint)	Patient medical records and CRF	Time (month) from the beginning of the response to progression or death from any cause + 1.
Duration Of	Time to Event	Patient medical	Time (month) from the first to last dose of avelumab + 1.

PFIZER CONFIDENTIAL

CT24-WI-GL03-RF02 2.0 Non-Interventional Statistical Analysis Plan For Primary Data Collection Study

01-Jun-2020

Page 12 of 28

Treatment (DOT)	Exposure	records and CRF	
Patterns of progression under avelumab	Outcome (secondary endpoint)	Patient medical records and CRF	Description of metastatic sites and type of progression (new lesion(s)/progression of known lesion(s)).
OS of subsequent treatment	Time to Event Outcome (secondary endpoint)	Patient medical records and CRF	Time (month) from the first injection of avelumab-subsequent treatment to death, whatever the reason +1
PFS of subsequent treatment	Time to Event Outcome (secondary endpoint)	Patient medical records and CRF	Time (month) from the first injection of avelumab-subsequent treatment to the date of progression or death from any cause +1.
ORR of subsequent treatment	Outcome (secondary endpoint)	Patient medical records and CRF	Proportion of participants with a Complete Response or Partial Response as a best response during the avelumab-subsequent treatment.
DOT of subsequent treatment	Time to Event Exposure	Patient medical records and CRF	Time (month) from the first to last dose of avelumab-subsequent treatment + 1.
FBISI-18 score evolution	Outcome (secondary endpoint)	NCCN/FACT FBISI-18	Absolute value and relative change from baseline of PRO evaluation at available timepoints
EQ-5D-5L score evolution	Outcome (secondary endpoint)	EQ-5D-5L	Absolute value and relative change from baseline of EQ-5D-5L scores at available timepoints
EQ VAS evolution	Outcome (secondary endpoint)	EQ-5D-5L	Absolute value and relative change from baseline of EQ VAS at available timepoints
Premedication's (acetaminophen and antihistamine)	Outcome (secondary endpoint)	Patient medical records and CRF	Proportion of participants who received a premedication at each injection of avelumab

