### 9.1.2. Secondary endpoints

- OS from the start of the chemotherapy used in 1st line: time between the first injection of the chemotherapy used in 1st line and the date of death from any cause.
- PFS1: time between the first injection of avelumab and the date of progression or death from any cause. Progression status will be defined according to RECIST 1.1.
- PFS2: time between the first injection of avelumab and the date of progression or death from any cause during the 2nd line of treatment post-avelumab. Progression status will be defined according to RECIST 1.1.
- ORR: proportion of patients with a Complete Response or Partial Response as a best response during the avelumab treatment. Responses to treatment will be defined according to RECIST 1.1.
- DOR: time between the beginning of the response and progression or death from any cause.
- DOT: time between the first and last dose of avelumab.
- Patterns of progression under avelumab: metastatic sites and type of progression (new lesion(s)/progression of known lesion(s)).
- Subsequent treatments and response to these treatments: DOT, PFS, ORR and OS.
- Safety: AEs of any type, grade 3-4 AEs, AEs leading to interruption or discontinuation, AEs leading to death.

090177e1a41aac13\Final\Final On: 28-Jul-2025 13:50 (GMT)

- Premedications (acetaminophen and antihistamine): Proportion of patients who received a premedication at each injection of avelumab. Median number of cycles with premedication. To evaluate the correlation between infusion-related reactions and premedication.
- Evolution of PROs NCCN/FACT FBISI-18 and EQ-5D-5L scores during avelumab treatment.

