### 9.3. Variables

Table 2 shows the information which will be collected in the study.

090177e1a41aac13\Final\Final On: 28-Jul-2025 13:50 (GMT)

Table 2. Information collected in the study and timing of data collection

Data elements	Variables	Timing of data collection		
		Inclusion	6 weeks	3 months, then every three months until end of follow-up
Inclusion	
 
Type of center
 
Eligibility criteria (inclusion/exclusion)
 
Date of provision of information letter
 
	X		X
Characteristics of patients and their cancer before avelumab initiation	
 
Demographics : month and year of birth, sex
 
Patient and Cancer characteristics: 
 
Localisation: upper/lower (bladder, urethra) urinary tract
 
Cancer characteristics: histological subtype including type of variant*, PD-L1 status and FGFR alteration with type of test and CPS score.
 
 
 
Localized cancer: date of diagnosis, type of treatment (adjuvant/neoadjuvant), regimen, dates of start and end, number of ChT cycles, complete response if neoadjuvant.
 
Adv/mUC: date of diagnosis, stage at ChT initiation, metastatic sites at ChT initiation, Karnowski index and ECOG at ChT initiation, type of ChT regimen, dates of start and end, number of ChT
 
	X		X

090177e1a41aac13\Final\Final On: 28-Jul-2025 13:50 (GMT)

	cycles, response at the end of ChT, date of start of partial or complete response if so.			
Initiation of avelumab	
 
• Patients characteristics : ECOG at initiation
 
• Biological exam: neutrophil, lymphocyte, haemoglobin, creatinine clearance
 
• Metastatic sites
 
• Date of first administration, dose
 
• Use of premedication (acetaminophen and antihistamine)
 
	X		X

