6.1.2 Objective response rate (ORR)

Best response will be calculated with all available response assessments, from study treatment initiation to treatment discontinuation (included) or end of study if no discontinuation.

PFIZER CONFIDENTIAL

CT24-WI-GL03-RF02 2.0 Non-Interventional Statistical Analysis Plan For Primary Data Collection Study

01-Jun-2020

Page 13 of 28

For best response, the following order will be used (from better outcome to worst)
Complete Response (CR) > Partial Response (PR) > Stable Disease (SD) > Not Estimable (NE) > Progressive Disease (PD).

6.1.3 **FBISI-18 score**

NCCN-FACT FBISI-18 is an 18-item questionnaire filled by the participant. The response to each of the 18 questions is evaluated using a 5-point scale ranging from 0='Not at all' to 4='Very much'. For items negatively framed, scores will be reversed for analysis so that higher scores translate a good quality of life.

6.1.4 **EQ-5D-5L score**

A participant's score at a specific timepoint will then go from 0 (0=severely symptomatic) to 72 (asymptomatic). For each participant, a unique Health state score will be created by combining the answer given to each of the 5 dimensions. This score will thus be ranging from 11111 (no problems in any domain) to 55555 (severe problems). This score will be after converted into EQ-5D single utility index values anchored at 0 for death and 1 for perfect health, by applying a formula download from the EQ-5D official website, that essentially attaches values (also called weights) to each of the levels in each dimension.

6.2 **SAFETY ENDPOINTS**

Adverse events (AE) reported during the study will be coded using the MedDRA terminology (SOC and PT) with the most recent version of MedDRA.

6.3 **COVARIATES**

Refer to [5.3](#).

7 **HANDLING OF MISSING VALUES**

Unless otherwise specified, all data will be evaluated as observed, and missing data will not be imputed.

- The objective response will be the only endpoint with a formal imputation of missing data. Participants who do not have a post-baseline radiographic tumour assessment due to early progression, who receive anti-tumour therapies other than the study treatments prior to reaching a CR or PR, or who die, progress, or drop out for any reason prior to reaching a CR or PR will be counted as non-responders in the assessment of OR. Each participant will have an objective response status (0: no OR; 1: OR).

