8.2.2.4 Objective response rate (ORR)

ORR will be described overall and by subgroup defined in section 5.3.

Participants who do not have a post-baseline radiographic tumor assessment due to early progression, who receive anti-tumor therapies other than the study treatments prior to reaching a CR or PR, or who die, progress, or drop out for any reason prior to reaching a CR or PR will be counted as non-responders in the assessment of OR. Each participant will have an objective response status (0: no OR; 1: OR). OR rate (ORR) is the proportion of participants with OR in the FAS.

ORR will be calculated along with the 2-sided 95% CI using the Clopper-Pearson method (exact CI for a binomial proportion as computed by default by the FREQ procedure using the EXACT option).

ORR will also be described by subgroup (See section 5.3 for subgroup definition).

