8.2.2.10 ORR of subsequent treatment

ORR will be described and analyzed according to the specifications mentioned in section [8.2.2.4](#).

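### Subsequent-treatment ORR inherits avelumab's denominator and non-responder clause unchanged, and the avelumab ORR rules do not say whether a response carried over from chemotherapy counts

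*SAP*

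**What the plan says.** **Entry.** Protocol 9.2.1 admits patients "whose disease has not progressed (ongoing stable disease, partial response or complete response) following completion of first-line platinum-based chemotherapy".

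**Avelumab ORR.** SAP 6.1.1 defines it as "Proportion of patients with a Complete Response (CR) or Partial Response (PR) as a best response during the avelumab treatment". SAP 6.1.2 takes the best of all assessments between avelumab start and discontinuation. Protocol 9.1.2 adds: "Responses to treatment will be defined according to RECIST 1.1". SAP 8.2.2.4 sets the denominator: "OR rate (ORR) is the proportion of participants with OR in the FAS". Its list of non-responders includes those "who receive anti-tumor therapies other than the study treatments prior to reaching a CR or PR", and those who progress, die or drop out before a CR or PR. SAP 8.2.2.5 starts DOR at the first CR or PR.

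**Subsequent-treatment ORR.** SAP 6.1.1 defines it on its own line, as CR or PR as best response during the treatment that follows avelumab. The whole of SAP 8.2.2.10 is one sentence: "ORR will be described and analyzed according to the specifications mentioned in section" 8.2.2.4. The summary table in SAP 8.2.5 lists the analysis set as FAS.

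**Data.** Among the first-line chemotherapy items, Table 2 in Protocol 9.3 lists "response at the end of ChT, date of start of partial or complete response if so". For avelumab initiation it lists metastatic sites, but no tumour measurements and no response status.

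**The concern.** There are two gaps, and the first is the firmer.

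First, the rules of 8.2.2.4 were written for avelumab. Applied unchanged to the next line, they use a denominator that includes patients who never received that line, and a non-responder clause triggered by the very treatment under assessment. The result could be far below the response rate among the patients treated.

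Second, this is a maintenance setting. Patients may already be in CR or PR when avelumab starts. If a persisting chemotherapy response can be recorded as a response on avelumab, ORR mixes two different things, and DOR may begin at an on-avelumab scan of an older response. Two sites, or two programmers, could follow the plan and reach different figures from the same patients.

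**Working it through.** The documents give no expected ORR and no ORR precision, so there is no planned figure to reproduce. The precision calculation in Protocol 9.5 concerns median OS and has no bearing here. The check is a reading of the text, followed by illustrations in which every rate is an assumption.

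**1. Subsequent-treatment ORR: the text**

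- SAP 8.2.2.1 identifies the study treatment as avelumab. SAP 8.2.2.8 defines subsequent treatment as the line after avelumab. Every patient on that line has therefore received anti-tumour therapy other than the study treatment.
- On a literal reading, the 8.2.2.4 clause classes as a non-responder every such patient who had no CR or PR before that therapy. The progression part of the clause also catches those who progressed on avelumab without a CR or PR.
- SAP 8.2.2.8 (OS) and 8.2.2.9 (PFS) restrict the analysis to FAS patients who took the subsequent line. SAP 8.2.2.10 has no such restriction.

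**2. Subsequent-treatment ORR: illustration**

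Assume N = 600 in the FAS (the protocol target), n = 200 starting a subsequent line, none with an earlier CR or PR, and a true ORR on that line of 20–40%. Intervals are Clopper-Pearson 95%, as in SAP 8.2.2.4.

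| Rule | ORR 20% | ORR 40% |
|---|---|---|
| Patients on the line as denominator | 40/200 = 20.0% (14.7–26.2) | 80/200 = 40.0% (33.2–47.1) |
| FAS as denominator | 40/600 = 6.7% | 80/600 = 13.3% |
| Literal non-responder clause, patients on the line | 0/200 = 0% (0–1.8) | 0/200 = 0% (0–1.8) |

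With n = 100 the FAS denominator gives 3.3–6.7%; with n = 300 it gives 10.0–20.0%.

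**3. Avelumab ORR: the text**

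- A patient in CR at entry and still recorded as CR on avelumab meets 6.1.1 and 6.1.2 as written.
- For a patient in PR at entry, the result depends on the reference scan. Measured from a scan before chemotherapy, an unchanged PR is still a PR. Measured from a scan at avelumab start, it need not be.
- Neither document names that scan. SAP 8.2.2.4 speaks of assessments after baseline without saying what baseline is.
- SAP 8.2.2.5 starts DOR at the first CR or PR, so the same uncertainty passes to DOR.

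**4. Avelumab ORR: illustration**

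Let s be the share entering in CR or PR, c the share of these recorded as CR or PR on avelumab through carry-over, and r = 10% the rate of new response, applied for simplicity to everyone else. Then

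ORR = s × [c + (1 − c) × r] + (1 − s) × r

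| c | s = 50% | s = 80% |
|---|---|---|
| 0 (new responses only) | 10.0% (7.7–12.7) | 10.0% (7.7–12.7) |
| 25% | 21.3% | 28.0% |
| 50% | 32.5% | 46.0% |
| 100% | 55.0% | 82.0% |

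For example, with s = 50% and c = 50%: 0.5 × (0.5 + 0.5 × 0.1) + 0.5 × 0.1 = 0.275 + 0.05 = 32.5%. The width of the range shows how much depends on c, which the plan leaves undetermined.

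**The case against.** **The definition of subsequent ORR is right.** SAP 6.1.1 places it on its own line, and a sensible programmer might follow that. The 8.2.5 table also writes FAS for subsequent OS and PFS, whose own sections restrict the population, so that label alone settles nothing. This makes 8.2.2.10 an unadapted cross-reference, not a deliberate choice. The conflict remains, because 8.2.2.10 is the section that specifies the analysis. A reader might infer that subsequent ORR will come out near zero. The documents do not show that: it requires the literal clause to override 6.1.1, and the clause spares patients with an earlier CR or PR.

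**RECIST 1.1 is invoked.** It is, and if sites read from a scan at avelumab start, a persisting PR need not count. A reader might infer that chemotherapy responses are counted as avelumab responses by rule, or that avelumab ORR will mostly describe chemotherapy. Neither is supported. The plan fails to exclude carry-over but does not prescribe it, and no document gives the share entering in response or how sites code it.

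**ORR by chemotherapy response is planned.** SAP 5.3 lists best response to first-line chemotherapy as a subgroup, and 8.2.2.4 applies those subgroups to ORR. This is a real partial safeguard, since carry-over is not the issue in SD patients. It is weakened because 8.2.5 enters NA for ORR subgroups, and because best response is not the same as status at avelumab start: 5.3 allows for a gap of more than 10 weeks.

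**Consequence.** SAP 4.1 and 4.2 set no hypotheses and make every analysis descriptive. That limits the importance of the point but does not remove it.

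**Conclusion.** The point on subsequent-treatment ORR holds as a defect in the text: the cross-reference brings in the wrong denominator and a non-responder clause that contradicts 6.1.1, and the population differs from that in 8.2.2.8 and 8.2.2.9. Under the assumed 200 of 600 patients and a true ORR of 20–40%, the reported figure would fall to 6.7–13.3% with the FAS denominator, or to 0% under the literal clause among patients with no earlier CR or PR.

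The point on avelumab ORR holds as an omission. A carried-over response can count: literally so for a persisting CR, and depending on the unnamed reference scan for a PR. With an assumed 10% rate of new response, ORR could lie between 10% and 82% across the assumed ranges. That range describes the ambiguity and is not a forecast.

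Both should be corrected before these endpoints are analysed.

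**What to change.** **SAP 8.2.2.10 and the 8.2.5 table.** Use as denominator the FAS patients who took one or more doses of subsequent treatment. Assess response from the start of that line. Let only progression, death, drop-out or further anti-tumour therapy that occurs after the start of that line and before a CR or PR make a non-responder. This is a wording change.

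**SAP 6.1.2, 8.2.2.4 and 8.2.2.5.** Keep the protocol's ORR, and name the assessment at or last before avelumab start as the reference. Report ORR and DOR by response at the end of chemotherapy (CR, PR, SD), which is already collected, and state that it is a proxy for status at avelumab start. Show maintained CR and PR separately from new or improved responses. Replace NA for ORR subgroups in 8.2.5 so that it agrees with 8.2.2.4.

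It would be tempting to count only a step up in category (SD to PR or CR, PR to CR) and to drop patients entering in CR. That would miss a new RECIST partial response in a patient who enters in PR, and it would depart from the protocol's endpoint and FAS, so it is not recommended.

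**Cost.** A little more analysis, and the ORR attributed to avelumab may look lower. Because Table 2 lists no tumour measurements at avelumab start, responses that sites have already coded cannot be re-derived centrally from the listed variables. The breakdown by chemotherapy response is therefore needed as well as the named reference.
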